Indicate which **variable(s)** will be assessed to judge the primary specific aim. Give measurement units, if applicable.

We will measure the following parameter:

- **Serum zoster antibody levels by gpELISA expressed in (units/ml)**

12.6 * Secondary Outcome(s)

Indicate which **additional variable(s)** will be assessed to judge the secondary outcome(s). Give measurement units, if applicable.

- **Interferon-stimulated gene (ISG) expression in PBMCs expressed as fold-change (FCH) above baseline**
- **Serum biomarkers of innate immune activation (expressed in %)**
- **Responder cell frequency: VZV specific CD4+ T cells post-vaccination (expressed in %)**
- **Interferon-gamma response by ELISpot expressed as number of spot-forming cells per 10^6 PBMCs**

12.7 * Methods and Procedures

Please provide a description of the laboratory and clinical analyses and procedures that will be performed. Include the role of external collaborators and consultants when appropriate. Please refer to Help text for Guidance.

This study is an open-label protocol divided into the healthy versus chronic HCV volunteer arms. The study will be advertised in local newspapers and different online resources. Potential participants identified with the aid of the Bellevue Hospital Center Hepatitis clinic and other local physicians, will be asked to call [name] ([name]), if they are interested in the study.

Our aim is to screen and enroll 20 age-matched (\pm 5 years) and gender-matched individuals between 50 and 60 years of age into each arm of the study. Individuals recruited into the study must be HIV and hepatitis B negative, without a history of vaccination within the past month, no history of immunosuppressive therapy, active malignancies or herpes zoster reactivation. Baseline screening tests (HIV ELISA, hepatitis B anti-surface and core antibodies, hepatitis C antibody, viral load and genotyping, complete blood counts and a comprehensive metabolic panel) will be obtained prior to enrolling in the study. HCV viral load and genotyping: will be determined by clinical laboratory analysis. Patient blood samples will be sent to a CLIA certified reference laboratory for analysis.

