The primary analysis for the set of primary outcomes will search for statistical evidence of impairment in the innate and adaptive immune response in chronic-HCV subjects compared to age-matched Healthy Controls by testing the hypotheses that the variation from baseline to day 42 will differ between these two groups. To achieve this goal, we will apply two-sided paired t-tests and/or Wilcoxon tests for each one of the outcomes. Additionally, as a secondary analysis, we will fit a mixed-effects model that will use group (HCV – HC) and time (0,3,7,14, and 42 days) as fixed effects and a random intercept for each subject. This modeling strategy allows to infer about differences across time points, and also within time points, while controlling for multiple testing. Further evaluation of the immune signature generated by the zoster vaccine will be done with flow cytometry and ELISpot assays and qualitative comparisons with other

human system immunology and /or vaccination studies will be carried out. For the secondary outcomes, the analysis for the ISG expressions as measured by RNA-seq counts will be processed in *limma* package in R and the same formulation for mixed-effects model described previously will be applied to verify differences at gene-wise level. Serum biomarkers of immune activation will be compared across groups with paired t-tests and Wilcoxon test for each time point.

12.9 * Explain the rationale for the choice of statistical measures and the number of participants proposed for the study, including the power calculations when applicable.

A sample of n=40 (20 HCV / 20 HC) individuals provides 80% power at 1.6% (after Bonferroni correction for 3 outcomes) significance to detect minimum differences in biomarkers variation from baseline to day 42 as 1.08 standard deviations when applying two-sided paired t-tests. Since there is no preliminary data showing the degree of variability in the primary outcomes for the chronic HCV population, this pilot study will be valuable for future power analysis. To test for gene-wise differences between healthy and HCV-infected groups for a single time point, a sample size of n=20 individuals in each groups provides 80% power at 5% significance to detect effect sizes greater than 1.5 FCH (Fold-Changes), assuming a coefficient of variation as 40% and a depth of coverage greater than 20. Calculation was performed using the library RNASeqPower in R software version 3.2.1.

12.10 * Will samples be coded?

Yes No

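### Sections 12.5 and 12.9 disagree on one or three primary outcomes; if three are kept, Holm's procedure would be a cheap gain over the Bonferroni level used for sizing

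*Combined protocol and SAP*

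**What the plan says.** Section 12.9 (rationale for the number of participants) starts from "A sample of n=40 (20 HCV / 20 HC) individuals" and states that this "provides 80% power at 1.6% (after Bonferroni correction for 3 outcomes) significance". The detectable effect is given as "minimum differences in biomarkers variation from baseline to day 42 as 1.08 standard deviations".

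Section 12.8 (Data Analysis) speaks in the plural: "The primary analysis for the set of primary outcomes" is to "search for statistical evidence of impairment in the innate and adaptive immune response", and for this "we will apply two-sided paired t-tests and/or Wilcoxon tests for each one of the outcomes". It does not count or name the outcomes in that set, and it gives no rule for declaring significance across them. Its one reference to controlling multiplicity belongs to the secondary mixed-effects model.

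Section 12.5 (Primary Outcome) is in the singular: "We will measure the following parameter", followed by one entry, "Serum zoster antibody levels by gpELISA expressed in (units/ml". Section 12.6 lists four further measures as secondary: interferon-stimulated gene expression, serum biomarkers of innate activation, VZV-specific CD4+ responder cell frequency and the interferon-gamma ELISpot.

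**The concern.** There are two linked questions.

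The first is what the correction is for. A division by three makes sense only if there are three primary tests, and section 12.5 lists one. Until that is settled, a reader cannot tell whether the antibody comparison will be judged at 1.6% or at 5%.

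The second applies only if there are three. A single-step Bonferroni level holds every outcome to 5%/3 whatever the others show. Holm's procedure compares the ordered p-values with 5%/3, 5%/2 and 5%, stopping at the first that fails. It has the same strong familywise control, needs no assumption about correlation, and rejects everything that Bonferroni rejects. With 20 per group, the difference can matter for the second and third outcomes. The stated 80% is also a figure for one outcome at a time, which section 12.9 does not say.

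**Working it through.** **Inputs.** From section 12.9: 20 per group, two-sided level 0.016 (0.05/3 = 0.01667, rounded down), three outcomes, a difference of 1.08 SD in the change from baseline to day 42, and power of 80%. The documents give no correlation between outcomes. I assume 0 to 0.6 and show 0.8 once as an extreme. No dropout allowance is stated and none is applied.

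**1. The plan's own figure.** For an unpaired two-sample t-test with 38 df, the noncentrality is 1.08 × √(20/2) = 3.415.

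| Two-sided level | Power at 1.08 SD | Detectable at 80% |
|---|---|---|
| 0.016 | 80.9% | 1.07 SD |
| 0.05/3 | 81.4% | 1.06 SD |
| 0.025 | 85.5% | 1.01 SD |
| 0.05 | 91.4% | 0.91 SD |

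The stated 80% and 1.08 SD are reproduced. A truly paired test on 20 pairs, with 1.08 read in SDs of the pair differences, would give 97.9% at 0.016. The plan's figure is therefore an unpaired one although the text says paired, and the steps below use the unpaired test.

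**2. Validity of the Bonferroni level.** 3 × 0.016 = 0.048, which is below 0.05.

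**3. One primary outcome.** If section 12.5 governs, the antibody test is made at 5%: power is 91.4% at 1.08 SD, or 80% at 0.91 SD. Holm then has nothing to step through.

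**4. Three outcomes, all effects 1.08 SD, independent.** This case can be done by hand. From the table, the chance that a p-value falls at or below 0.0167 is A = 0.8136; between 0.0167 and 0.025, B = 0.8554 − 0.8136 = 0.0418; between 0.025 and 0.05, C = 0.9143 − 0.8554 = 0.0589; above 0.05, D = 0.0857.

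- Bonferroni, all three: A³ = 0.539.
- Holm, all three: A³ + 3A²B + 3AB² + 3A²C + 6ABC = 0.5386 + 0.0830 + 0.0043 + 0.1170 + 0.0120 = 0.755.
- Holm, exactly two: 3A²D + 6ABD = 0.188.
- Holm, exactly one: 3A(C + D)² = 0.051.
- Holm, per outcome: (3 × 0.755 + 2 × 0.188 + 0.051)/3 = 0.897, against 0.814 with Bonferroni.
- At least one rejection, either method: 1 − (1 − A)³ = 0.994.

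**5. Other patterns, by simulation** (200,000 trials per setting, unpaired t-tests, Bonferroni at 0.05/3):

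| Real effects | Correlation | Per real outcome, Bonferroni → Holm | At least one rejection (both methods) |
|---|---|---|---|
| 3 | 0 | 81% → 90% | 99.4% |
| 3 | 0.5 | 81% → 88% | 95.7% |
| 3 | 0.8 | 81% → 87% | 91.2% |
| 2 | 0 | 81% → 85% | 96.7% |
| 2 | 0.5 | 81% → 84% | 92.7% |
| 1 | 0 | 81.4% → 81.5% | 82.0% |
| 1 | 0.5 | 81.3% → 81.5% | 82.3% |

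A further run at correlation 0.6 gives 88% per outcome with three real effects and 84% with two. With three real effects, rejection of all three goes from 54% to 75% at correlation 0 and from 65% to 80% at 0.6.

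**6. Error rate.** The familywise error under Holm is at most 5% within simulation error in every setting. With no real effects it is 5.0% at correlation 0 and 4.5% at 0.5, the same as Bonferroni at 0.05/3. With one real effect it is 4.7% and 4.2%.

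**7. Sample size.** Holm's first step uses the same 0.05/3 level, so 20 per group and 1.08 SD stand.

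**The case against.** Several objections carry weight.

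- **The premise may be false.** Section 12.5 lists one primary outcome. Writing Holm into the plan without settling this would fix the number at three by default. This stands, and it sets the order of the fix.
- **Bonferroni appears only in the sizing argument.** A plan that meant to use Holm could also be sized at 5%/3. A reader might infer that each primary test will be judged at a fixed Bonferroni level. That is the natural reading, because no other rule is given, but section 12.8 does not say so. What the documents support is that the decision rule is missing.
- **The largest gain needs all three effects to be real.** This stands. The documents give no expected effects for these outcomes, and with one real effect the gain is negligible.
- **The hypothesis joins innate and adaptive responses.** A reader might infer that all three outcomes must be significant, so that the plan's real power is 54-65%. No section makes that the success criterion, and the three outcomes are unnamed, so none can be called innate or adaptive. If all three were required, each could be tested at 5% with no correction, with power of 0.9143³ = 76% at correlation 0, slightly above Holm's 75%.
- **The calculation is unpaired and the text says paired.** Under the paired reading in the working, Bonferroni power is already about 98% per outcome and Holm adds about one point. The gain is therefore tied to the calculation that reproduces the stated 80%.
- **This is a pilot and Bonferroni is valid.** Both are true, so the choice of Holm is optional.

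**Conclusion.** The point holds in a limited form. The firm part is that sections 12.5, 12.8 and 12.9 do not agree on how many primary outcomes there are, that the three behind the correction are unnamed, and that section 12.8 has no multiplicity rule for the primary tests.

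The Holm part is conditional on keeping three. In that case it gives 7 to 9 points of power per outcome if all three effects are real, 3 to 4 if two are, and essentially none if one is. It adds nothing to the chance of at least one rejection. These figures assume 1.08 SD for each real effect, correlation of 0 to 0.6 and an unpaired test.

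A reader might go further and conclude that the Bonferroni level is a mistake, or that Holm is free. Neither is supported. Three tests at 1.6% keep the familywise error within 5%, and Holm does not come with the simple matching simultaneous intervals that Bonferroni has.

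**What to change.** 1. Make sections 12.5, 12.8 and 12.9 name the same primary outcome or outcomes.
2. If antibody alone is primary, remove the correction from section 12.9, restate the detectable difference at 5% (0.91 SD for 80% power, unpaired), and treat the other measures as secondary.
3. If three are kept, name them in section 12.5 and state in 12.8 that they are tested by Holm's procedure at a familywise 5%, with the ordered p-values compared with 1.67%, 2.5% and 5%, stopping at the first that fails. In 12.9, keep 1.08 SD as the first-step figure and say that 80% is the power for one outcome.
4. State whether the power figure is for a paired or an unpaired test, so that it matches the analysis.

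The cost is a few sentences, with no change in sample size. Under Holm, simultaneous intervals will not match the tests exactly. Bonferroni intervals can still be reported beside them, with a note that they are the more conservative.

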Chronic HCV infection is associated with persistent innate immune activation and dampened cellular immune responses. Interferons (IFNs) are key mediators of the antiviral innate immune response, initiating expression of interferon-stimulated genes (ISGs) with numerous host protective effector functions. In chronic HCV, high pre-therapy expression of ISGs and persistent activation of the innate immune system negatively predict the response to IFN-based therapies and failure of viral clearance. Innate immune response will be determined by RNA-seq pre- and post-vaccination. RNA will be isolated using commercially available PAXgene tubes to immediately stabilize intracellular RNA profile, in addition to the traditional homogenization of isolated volunteer PBMCs in Trizol prior to cryopreservation. Blood will be collected into PAXgene tubes and isolated PBMCs will also be collected into TRIZOL for RNA isolation and RNA-seq analysis. RNA isolated from PBMC will be prepared by the Genomic Resource center and sequenced for genome-wide mRNA expression profiling. Genome-wide mRNA expression profiles will be compared between the two arms of the study (healthy and chronically HCV infected volunteers). Gene expression levels will be quantified in relation to a reference standard of External RNA Control Consortium (ERCC) controls – a calibrated panel of defined RNA molecules at defined concentrations that will be “spiked in” to each library preparation to serve as a universal reference across samples.

PBMC samples may also be analyzed by single cell resolution InDrop RNA-Seq (REFERENCE PMID: 26000487), established for immune response profiling in the [name] laboratory. Within a microfluidic device, individual cells and individual hydrogel “barcode beads” are co-encapsulated in water-in-oil droplets, in which reverse transcription tags nascent cDNA with cell-specific barcode sequences. After droplet breakage, library preparation and high throughput sequencing, reads can be assigned to individual cells by barcode for gene expression profiling. Using this approach, sufficient sampling can be achieved with relatively low input cell numbers and rare cells (i.e. dendritic cells, antigen-specific lymphocytes) are represented in resulting datasets.

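### The ISG outcome is change from baseline, but the gene-wise model names no group-by-time term and the 80% RNA-seq power covers only a single-visit comparison

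*Combined protocol and SAP*

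**What the plan says.** **Outcome (12.6).** The first secondary outcome is "Interferon-stimulated gene (ISG) expression in PBMCs expressed as fold-change (FCH) above baseline". Each participant is measured against their own day 0.

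**Aim (12.4, Aim 2).** Innate activation is to be judged from how ISG expression changes between the pre- and post-vaccination samples. The same aim also plans a comparison of genome-wide expression profiles between the two arms.

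**Model (12.8).** RNA-seq counts are to be processed in limma and analysed gene by gene with the mixed model set out earlier in that section: fixed effects for group and for time (days 0, 3, 7, 14 and 42) and a subject-level random intercept. No interaction is named. The model is said to support inference both across and within time points, with control for multiple testing.

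**Power (12.9).** The RNA-seq statement is framed as "To test for gene-wise differences between healthy and HCV-infected groups for a single time point". It says that "a sample size of n=20 individuals in each groups provides 80% power at 5% significance" for fold-changes above 1.5, "assuming a coefficient of variation as 40% and a depth of coverage greater than 20". No correlation between a participant's baseline and later samples is given, and no power is given for a between-group difference in change.

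**Background (12.7).** Chronic HCV is described as a state of lasting innate immune activation, and the text goes on to discuss "In chronic HCV, high pre-therapy expression of ISGs and persistent activation of the innate immune system" as predictors of poor response to interferon-based therapy.

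**The concern.** The hypothesis in 12.3 is that people with chronic HCV respond less well to the vaccine. For an outcome defined as change from baseline, that is a statement about the difference between groups in change. It needs a term that lets the two groups follow different courses over time.

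A model with group and time main effects only has one group difference, the same on every day including day 0, and one time course shared by both groups. The group coefficient is a difference in level averaged over all visits. The time coefficients are changes averaged over both groups. Neither measures a difference in change.

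This matters because the protocol's own background suggests that ISG levels may already differ before vaccination. A group effect, or a difference at one post-vaccination visit, could then be read as an altered vaccine response when it was there on day 0. The power statement has the same gap: it describes a difference in level at one visit, and a reader may take its 80% to cover the outcome in 12.6.

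**Working it through.** **1. Inputs.** From 12.9: n = 20 per group, alpha 5%, fold-change 1.5 (ln 1.5 = 0.405), CV 0.40, depth above 20 (taken as exactly 20 unless stated). Assumed: two-sided test, normal approximation, no multiplicity adjustment, independent groups, no dropout, same CV and depth at both visits.

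**2. The plan's own figure.** The log-expression variance at one visit is 1/depth + CV² = 0.05 + 0.16 = 0.21.

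n per group = 2(1.960 + 0.842)² × 0.21 / 0.405² = 20.05

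Power at n = 20 is 79.9% and the smallest detectable fold-change is 1.50. The stated 80% is reproduced for the single-visit comparison.

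**3. Variance for change from baseline.** Let ρ be the within-person correlation of the biological component. Counting noise is independent at the two visits, so it enters twice:

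V = 2(1 − ρ)CV² + 2/depth = 0.32(1 − ρ) + 0.10 at depth 20

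**4. Power for a 1.5-fold ratio between the groups' fold-changes.** Power = Φ(0.405/√(2V/20) − 1.960). The detectable ratio at 80% power is exp(2.802 × √(2V/20)).

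| ρ (biological) | V | Power, n = 20 per group | Ratio detectable at 80% | n per group for 80% |
|---|---|---|---|---|
| 0.3 | 0.324 | about 62% | 1.66 | 31 |
| 0.5 | 0.260 | 71% | 1.57 | 25 |
| 0.8 | 0.164 | 89% | 1.43 | 16 |

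Over the wider range from ρ = 0 to ρ = 0.9, power runs from 51% to 94%.

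**5. Correlation at which change has the stated 80%.** Set V = 0.21: 0.32(1 − ρ) = 0.11, so ρ = 0.656, about 0.66. If the correlation is instead that of total log expression, counting noise included, then 2(1 − ρ) × 0.21 = 0.21 gives ρ = 0.5. These are the same point on two scales: 0.656 × 0.16/0.21 = 0.50.

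**6. Effect of depth.** The plan says depth is above 20. At depth 50, V = 0.32(1 − ρ) + 0.04. Setting V = 0.21 gives 1 − ρ = 0.17/0.32 = 0.531, so ρ of about 0.47 suffices for 80%. At ρ = 0.5, V = 0.20 and power is about 82%.

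**7. What the model can estimate.** Write expected log expression as μ + group + time. The change from day 0 to day t is then time(t) − time(0) in both groups, so the between-group difference in change is zero by construction. With a group-by-time term, that difference becomes a parameter for each post-vaccination day and can be tested.

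**The case against.** The strongest reply is that the single-visit comparison is itself planned. Section 12.8 speaks of differences within time points, Aim 2 compares expression between arms, and 12.9 says openly which contrast it powers. This stands. A reader might infer that the RNA-seq power is miscalculated, or that it belongs to no planned analysis. The documents support neither: the figure reproduces, and it belongs to a contrast the plan intends to examine.

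A second reply is that inference both across and within time points makes little sense without an interaction, so one was probably meant. That is plausible. But the fixed effects are listed explicitly and the interaction is not among them, so the test of the defined outcome rests on the analyst's reading. Nor does the fold-change definition rescue the model, because 12.8 applies it to RNA-seq counts with day 0 among the time points.

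Third, a reader might infer that the study is underpowered for the ISG outcome. The documents do not show that. They give no within-person correlation, and a high correlation or greater depth would put power above 80%. The 0.66 threshold applies only to the biological correlation at depth exactly 20.

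Fourth, the sentence on pre-therapy ISG expression concerns response to interferon-based treatment and does not compare HCV patients with healthy people. This also stands: raised baseline ISGs relative to the controls are an inference from the described innate activation, not a stated finding. The need for the interaction does not depend on that inference; it follows from the outcome definition.

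**Conclusion.** The concern holds as a mismatch between the defined ISG outcome and the model and power statement attached to it. As written, the gene-wise model has no term for a between-group difference in change from baseline, and the 80% power does not describe that contrast. There is no arithmetic error, and no power shortfall is demonstrated.

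The size is a range. At depth 20 and unadjusted two-sided 5%, power for a 1.5-fold ratio of fold-changes is about 62% to 89% as the biological correlation goes from 0.3 to 0.8, and it is higher at greater depth. This rests on the assumptions listed with the inputs, above all on a correlation that the documents do not supply.

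Severity is minor to moderate: the outcome is secondary, the study calls itself a pilot, and the sample size for the primary outcome is unaffected.

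**What to change.** 1. **Section 12.8.** Add group-by-time to the limma/mixed-model specification. Name the between-group difference in post-minus-baseline log expression, at a stated day, as the test for the ISG outcome. Keep the within-time-point comparisons as additional analyses, labelled as differences in level.
2. **Section 12.9.** State that the 80% applies only to the single-visit comparison. Add power for the change contrast over a range of correlations, such as 0.3 to 0.8, and at more than one depth. Say whether the correlation refers to the biological component or to total log expression.

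The cost is one extra model term, a few sentences, and a stated power that may look less favourable if the correlation is low. No additional participants, visits or samples are needed.
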